## 1.2 Purpose

The purpose of this Phase 2 study is to evaluate the efficacy, safety, and tolerability of oral remibrutinib (LOU064) at doses of CCI [REDACTED] for one month (4-5 weeks), and oral remibrutinib CCI [REDACTED] for 1 week compared to placebo in adult participants (age 18-55 years, inclusive). Assessments will serve to measure protection against allergic reaction by measuring the decrease of sensitivity (e.g.: signs and symptoms of allergic reaction) to oral peanut allergen administered in a double-blind, placebo-controlled food challenge (DBPCFC). Participants will have medically confirmed peanut allergy. Data from this study will be used to support the registration of remibrutinib use in the food allergy population to protect against allergic reactions due to an accidental exposure to peanut.

## 2 Objectives, endpoints and estimands

**Table 2-1 Objectives and related endpoints**

Objective(s)	Endpoint(s)
Primary objective(s)	Endpoint(s) for primary objective(s)

 
To evaluate the efficacy of oral remibrutinib CCI compared to placebo, as measured by the proportion of participants who can tolerate a single dose of <math>\geq 600</math> mg (1044 mg cumulative tolerated dose) of peanut protein without dose-limiting symptoms during the DBPCFC (Section 16.4, Table 16-7) at one month
 
	
 
Responder status defined as tolerating a single dose of <math>\geq 600</math> mg (1044 mg cumulative tolerated dose) of peanut protein without dose-limiting symptoms during the DBPCFC conducted at one month (Section 2.1 Primary Estimands)
 

Secondary objective(s)	Endpoint(s) for secondary objective(s)

 
To evaluate the efficacy of oral remibrutinib CCI compared to placebo, as measured by the proportion of participants who can tolerate a single dose of <math>\geq 1000</math> mg (2044 mg cumulative tolerated dose) of peanut protein without dose-limiting symptoms during the DBPCFC at one month
 
To evaluate the efficacy of oral remibrutinib CCI compared to placebo, as measured by the proportion of participants who can tolerate a single dose of 3000 mg (5044 mg cumulative tolerated dose) of peanut protein without dose-limiting symptoms during the DBPCFC at one month
 
To evaluate the efficacy of oral remibrutinib CCI compared to placebo, as measured by the maximum symptom severity at any single challenge dose up to and including 1000 mg of peanut protein during the DBPCFC at one month
 
To evaluate the efficacy of 3 weeks of placebo treatment followed by 1 week of oral remibrutinib CCI treatment compared to one month of placebo treatment, as measured by the proportion of participants who can tolerate a single dose <math>\geq 600</math> mg of peanut protein without dose-limiting symptoms during the DBPCFC at one month
 
	
 
Responder status defined as tolerating a single dose of <math>\geq 1000</math> mg (2044 mg cumulative tolerated dose) of peanut protein without dose-limiting symptoms during the DBPCFC conducted at one month
 
Responder status defined as tolerating a single dose of 3000 mg (5044 mg cumulative tolerated dose) of peanut protein without dose-limiting symptoms during the DBPCFC conducted at one month
 
Maximum severity of symptoms occurring at any challenge dose of peanut protein up to and including 1000 mg during the DBPCFC conducted at one month. Symptom severity will be categorized as 4 levels: None, Mild, Moderate, Severe
 
Responder status defined as tolerating a single dose of <math>\geq 600</math>mg (1044 mg cumulative tolerated dose) of peanut protein without dose-limiting symptoms during the DBPCFC conducted at one month (3 weeks of placebo + 1 week of remibrutinib treatment vs. one month of placebo)
 

Objective(s)	Endpoint(s)


• To evaluate the effects of multiple doses of remibrutinib compared to placebo (when applicable), as measured by multiple systemic biomarkers to inform on response to treatment or disease severity

• To evaluate the safety and tolerability of multiple doses of remibrutinib

• To assess the ability of remibrutinib to impact skin mast cells through the assessment of allergen-specific skin prick test (SPT)

• To assess the pharmacokinetics (PK) of remibrutinib

	

• Change from baseline at Weeks 1 and 4 of:

• peanut-specific IgE, including peanut components

• peanut-specific IgG4, including peanut components

• Treatment-emergent adverse events, vital signs, ECG, and laboratory values, including immunoglobulin levels

• Change from screening in SPT mean wheal diameters at one month

• Remibrutinib concentrations in blood and PK parameters (including, but not necessarily limited to: Cmax, AUClast, AUCtau, Tmax)

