**Study drug must be administered prior to DBPCFC at end-of-treatment visits on Days 26 and 28.**

For visits that do include pharmacokinetic sampling (Days 8 and 25), every effort will be made to take the pharmacokinetic sample at the protocol specified time points. ECG in triplicate is required pre and post dose on these visits. The order of assessments on PK visit days is: ECG (in triplicate), pre-dose PK blood draw, dosing at 0h followed by ECG after dosing but before 0.5h PK blood draw timepoint.

Please ensure the order of assessments is respected consistently.

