##### 8.5.2 Pharmacokinetics

PK samples will be collected at the visits and timepoints defined in the assessment schedule (Table 8-1).

PK assessment will be limited to 6 time points at each visit to characterize peak exposures of remibrutinib (0, 0.5, 1, 2, 3, 4 hours after intake of study medication, respectively). Samples should be taken as close to the given time (0, 0.5, 1, 2, 3, 4 hours post dose) as possible and the sampling time must be recorded. CCI

PK samples will be obtained and evaluated in all participants on active treatment. Follow instructions outlined in the laboratory manual regarding sample collection, numbering, processing and shipment.

All samples will be given a unique sample number as per lab manual. The actual sample collection date and time will be entered on the appropriate eCRF page.

CCI

If participants cannot visit the site for protocol specified PK assessments (per Section 4.6), an alternative collection method (e.g. home nursing) may be used if available. Samples should then be sent to site for processing and shipment as per a normal site visit.

Remibrutinib blood concentrations will be determined by a validated Liquid Chromatography-Mass Spectrometry (LC-MS/MS) method. Concentrations will be expressed in mass per volume units (ng/mL) and will refer to the free base. Concentrations below the LLOQ will be reported as “zero” and missing data will be labeled as such in the Bioanalytical Data Report.

The number of samples/blood draws collected will not exceed those stated in the protocol.

A non-validated method will be used for metabolite investigations as needed.

For standard PK abbreviations and definitions see the list provided at the beginning of this protocol. The following PK parameters will be determined from the blood concentration time data using the actual recorded sampling times and non-compartmental method(s) with Phoenix WinNonlin (Version 6.4 or higher): Cmax, Tmax, AUClast, AUCtau. Additional PK parameters may be determined as needed.

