The linear trapezoidal rule will be used for AUC calculation. Regression analysis of the terminal plasma elimination phase for the determination of T1/2 will include at least 3 data points after Cmax. If the adjusted R^2 value of the regression analysis of the terminal phase will be less than 0.75, no values will be reported for T1/2, AUCinf, Vz/F and CL/F. Therefore, and due to the limited sampling up to 4 hours these PK parameters may not be determined.

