**Figure 12-1**

CCI

Optimal contrasts will be derived for the remibrutinib BID dose regimen dose-response curves according to the model shapes above.

The global test decision is based on the maximum of all contrast test statistics from the proposed candidate shapes. A critical value  $q$  controlling the type I error rate can be derived from the fact that the contrast test statistics approximately follow an asymptotic multivariate normal distribution. If the maximum contrast test statistic exceeds the critical value  $q$ , the overall null hypothesis of a constant dose-response curve is rejected and proceeds to the estimation steps to determine the dose-response curve.

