**List of abbreviations**

---

AE	Adverse Event
AESI	Adverse Event of special interest
AIC	Akaike information criterion
ANCOVA	Analysis of Covariance
AUClast; AUCtau	Area under (the) curve up to last time point; for the dosing interval
CCI	
CCI	
BMI	Body mass index
Bpm	Beats per minute
CI	Confidence Interval
CM	Concomitant medication
Cmax	Maximum blood concentration
COVID-19	Coronavirus disease (2019)
CRO	Contract Research Organization
CRF	Case Report Form
CRS	Case Retrieval Strategy
CTCAE	Common terminology criteria for adverse event
CV	Coefficient of Variation
DB(L)	Database (lock)
DBPCFC	Double-Blind Placebo Controlled Food Challenge
CCI	
ECG	ElectroCardioGram
ED	Effective dose
Emax	Maximum effect
EOS	End of study
HMC	Hamiltonian Monte Carlo
IA	Interim Analysis
ICH-GCP	ICH guideline for good clinical practice
IgE	Immunoglobulin E
IgG	Immunoglobulin G
LLN	Lower level of normal
LLOQ	Lower Limit of Quantification
MAR	Missing At Random
CCI	
MedDRA	Medical Dictionary for Drug Regulatory Affairs
MCP-Mod	Multiple Comparison Procedure – Modelling
ML	Maximum Likelihood
MTD	Maximum Tolerated Dose
OFC	Oral food challenge
PK/PD	Pharmacokinetics/Pharmacodynamics
PT	Preferred Term
RAP	Reporting & Analysis Process
SAE	Serious Adverse Event
SAP	Statistical Analysis Plan
SAS	Statistical Analysis System

---

---

SD	Standard Deviation
SMQ	Standardized MedDRA Query
SOC	System Organ Class
SPT	Skin Prick Test
TFLs	Tables, Figures, Listings
CCI	
Tmax	Time to reach maximum blood concentration
ULN	Upper limit of normal
ULOQ	Upper Limit of Quantification
WHO	World Health Organization

---

[figure not shown]

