## 2.8 Pharmacokinetic endpoints

Descriptive statistics of remibrutinib blood concentration data will be provided by treatment arm, and visit/sampling time point, including the frequency (n, %) of concentrations below the LLOQ and reported as zero. Summary statistics will include mean (arithmetic and geometric), SD, CV (arithmetic and geometric), median, minimum, and maximum. Concentrations below LLOQ will be treated as zero in summary statistics and for PK parameter calculations.

Relevant PK parameters will be listed by treatment arm and participant. Descriptive summary statistics for PK parameters will be provided by treatment arm. An exception to this is Tmax where median, minimum and maximum will be presented. PK analysis set will be utilized for all summaries and figures.

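### Setting values below LLOQ to zero breaks the planned geometric PK summaries, and AUCtau is named with no visible rule for the unsampled part of the dosing interval

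*Protocol*

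**What the plan says.** **Endpoint.** Protocol Table 2-1 lists "Remibrutinib concentrations in blood and PK parameters (including, but not necessarily limited to: Cmax, AUClast, AUCtau, Tmax" and SAP Table 1-1 repeats it. The SAP abbreviation list explains AUClast and AUCtau as "Area under (the) curve up to last time point; for the dosing interval".

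**Sampling.** Protocol 8.5.2: "PK assessment will be limited to 6 time points at each visit to characterize peak exposures of remibrutinib", at "0, 0.5, 1, 2, 3, 4 hours after intake of study medication, respectively". The visits are Days 8 and 25. Protocol Section 8 makes the 0 h sample a trough, since the order is "pre-dose PK blood draw, dosing at 0h followed by ECG after dosing but before 0.5h PK blood draw timepoint".

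**Interval.** Most dosing-frequency text is redacted, but Protocol 12.4.2 says "Optimal contrasts will be derived for the remibrutinib BID dose regimen dose-response curves". Protocol 6.2.4.1 fits this: the time of the previous night's dose is recorded before PK days.

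**AUC rules.** Protocol 8.5.2 sets the linear trapezoidal rule and requires at least 3 points after Cmax for a terminal slope. It suppresses half-life, AUCinf, Vz/F and CL/F when adjusted R² is below 0.75, and adds "Therefore, and due to the limited sampling up to 4 hours these PK parameters may not be determined". AUCtau is not in that list.

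**Values below LLOQ.** Protocol 12.5.3 and SAP 2.8 plan arithmetic and geometric means and CVs, tabulate the frequency of values below LLOQ, and state "Concentrations below LLOQ will be treated as zero in summary statistics and for PK parameter calculations".

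**The concern.** The zero rule and the geometric statistics cannot both be applied. A programmer who meets a zero must report a geometric mean of zero, report nothing, or drop the zero and average only the quantifiable participants. The last choice overstates the typical concentration, and nothing in the output would say it had been made. Both documents expect such values, because they tabulate their frequency.

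For AUCtau, about two thirds of the interval is unsampled. An analyst could extrapolate from a terminal slope or reuse the pre-dose value. The two routes differ in error and in which participants end up missing. The protocol doubts the slope after 4 h of sampling, but the visible text neither extends that caution to AUCtau nor says that AUCtau avoids the slope.

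**Working it through.** The plan states no figure to reproduce here. LLOQ, the rate below LLOQ and half-life are not given, so they are assumed over a range.

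**1. Zeros in geometric statistics**

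Geometric mean = exp[(1/n) Σ ln xᵢ]; geometric CV = √(exp(s²) − 1), where s is the SD of ln x. One xᵢ = 0 gives ln 0 = −∞. The geometric mean then collapses to 0 (product form) or fails (log form), and s does not exist.

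The chance that a cell has at least one such value is 1 − (1 − p)ⁿ, assuming independence. Protocol 12.8 expects 14 to 16 completers per one-month arm and 7 to 8 in the one-week arm.

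| assumed p | n = 14 | n = 7 |
|---|---|---|
| 1% | 13% | 7% |
| 5% | 1 − 0.95¹⁴ = 51% | 30% |
| 10% | 77% | 52% |
| 20% | 96% | 79% |

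Invented example: 14 participants, 10 at 5 × LLOQ and 4 below LLOQ.
- Rule as written: 0, or undefined.
- Zeros dropped: 5.0 × LLOQ.
- LLOQ/2: exp[(10 ln 5 + 4 ln 0.5)/14] = exp(13.32/14) = 2.59 × LLOQ.
- Dropped against LLOQ/2: 5.0/2.59 = 1.93-fold.

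**2. AUCtau**

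Sampled share of a 12 h interval: 4/12 = 33% of the time.

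Points left after the observed peak: 3 if it is at 1 h, 2 at 2 h, 1 at 3 h, 0 at 4 h. A slope that meets the 3-point rule therefore needs a peak at 1 h or earlier.

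Model (assumed): one compartment, oral, steady state, τ = 12 h, ke = ln 2/half-life,

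C(t) = ka/(ka − ke) × [e^(−ke·t)/(1 − e^(−ke·τ)) − e^(−ka·t)/(1 − e^(−ka·τ))].

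With the pre-dose value C₀ placed at 12 h, the linear rule gives AUCtau ≈ AUC0-4 + 8 × (C₄ + C₀)/2. As ratios to the true AUC0-12, with ka = 2.5/h:

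| half-life | AUC0-4 alone | C₀ at 12 h | zero at 12 h |
|---|---|---|---|
| 1 h | 0.89 | 1.13 | 1.12 |
| 2 h | 0.70 | 1.14 | 1.11 |
| 4 h | 0.53 | 1.06 | 0.95 |
| 8 h | 0.43 | 1.02 | 0.82 |

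When ka is varied so that the peak falls at 0.5 to 3 h where the model allows, the ranges are 0.37 to 0.93, 1.00 to 1.18 and 0.76 to 1.18.

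The last column shows why a pre-dose value below LLOQ should not be entered as zero. In that term C₀ is multiplied by 8/2 = 4 h, so the zero rule removes at most 4 h × LLOQ. That is small for profiles well above LLOQ and material only for profiles close to it.

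**3. The one-week arm**

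Protocol Section 3 gives this arm its first remibrutinib on Day 22. Its Day 8 profile is on placebo, so only Day 25 can supply a remibrutinib AUC.

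**The case against.** The strongest reply is that AUCtau needs no terminal slope. The pre-dose sample and the recorded previous-night dose time are what a steady-state approximation requires. The suppressed parameters all depend on the slope, so leaving AUCtau off that list may be deliberate. Parts of Protocol 8.5.2 are redacted, and a completion rule may sit there. AUClast is already an endpoint and equals AUC0-4h whenever the 4 h sample is quantifiable. The PK summaries are descriptive, and the count below LLOQ, median, minimum and maximum appear beside the geometric mean.

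Most of this stands for AUCtau. A reader might infer that AUCtau cannot be derived at all, or that it will be missing selectively in slow absorbers. The documents do not support either, because the second follows only if the slope is used. What remains is that the visible text leaves the method open.

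The reply does not rescue the zero rule. That conflict is in unredacted text in both documents, and showing the count does not make the geometric statistics computable.

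**Conclusion.** Wrong as written, limited to descriptive secondary PK.

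The LLOQ conflict is certain in kind: it occurs in every cell with at least one value below LLOQ and in no other. A reader might infer that all the planned geometric means are undefined; cells without such values are unaffected. How many cells are hit depends on a rate the documents do not give.

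The AUCtau point is smaller. The completion method is not visible, and a reasonable slope-free method carries an error of about 0 to 18% upward. That figure rests on a one-compartment steady-state profile, a 12 h interval, half-lives of 1 to 8 h and the linear rule.

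A reader might also infer that exposure would be overstated most in the lowest-dose arm, that the dose-exposure relation would be flattened, or that paediatric dose selection and registration would be harmed. The documents give no rates by dose. PK/PD modelling has its own analysis plan, and nothing says it uses these summary tables. The responder analysis does not use PK data.

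**What to change.** 1. In Protocol 12.5.3 and SAP 2.8, keep zero for arithmetic statistics and the median, and exempt geometric mean and geometric CV. State one convention before lock. For example, use LLOQ/2, report the geometric statistics only where at least half the values in the cell are quantifiable, and otherwise mark them not reported. Print the count below LLOQ beside each.
2. In Protocol 8.5.2 and SAP 2.8, name AUClast (AUC0-4h) as the observed exposure measure. If AUCtau stays, label it approximate and derive it from the pre-dose value at the end of the interval. Do not use a slope that fails the 3-point or adjusted R² 0.75 criteria.
3. Do not enter a pre-dose value below LLOQ as a true zero at the end of the interval. State the substitute, or report AUCtau as not determined for that profile.
4. Exclude Day 8 from AUCtau for the arm that takes placebo for three weeks.
5. If the change is made only in the SAP, record it in SAP Section 4, which now reports no changes.

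Cost: wording and programming, with no new samples. AUCtau is then claimed only as approximate, and some geometric statistics will not be reported.

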## 2.1 Primary estimands

The estimand is the precise description of the treatment effect and reflects strategies to address events occurring during trial conduct which could impact the interpretation of the trial results (e.g. premature discontinuation of treatment). The primary clinical question of interest is to understand the treatment effect of remibrutinib over placebo among participants who have completed DBPCFC after one month (4-5 weeks) of treatment and regardless of intake of rescue medication prior to DBPCFC at one month.

The primary estimand is described by the following attributes to address the primary clinical question of interest:

- **Population:** Participants aged 18 – 55 years, inclusive, who have been diagnosed with IgE- mediated confirmed peanut allergy and met study inclusion/exclusion criteria and have undergone DBPCFC at one month (4-5 weeks). Further details about the population are provided in [Section 5](#).
- **Variable:** Responder status defined as tolerating a single dose of  $\geq 600$  mg (1044 mg cumulative tolerated dose) of peanut protein without dose-limiting symptoms during the DBPCFC conducted at one month (4-5 weeks). The cumulative tolerated dose is the sum of the tolerated doses, not including the reactive dose ([Casale et al 2019](#)). Dose-limiting symptoms indicate a true allergic reaction occurring during administration of a single dose of peanut protein at the DBPCFC that should preclude the administration of any further doses in the view of the investigator.
- **Treatment:** The randomized treatment (one of five arms specified in [Section 6.1.3](#)) plus rescue medication (e.g., epinephrine, SABA, and/or anti-histamines) prior to DBPCFC at one month, if needed. Further details about the randomized treatment and rescue medication are provided in [Section 6.1](#) and [Section 6.2](#).
- **Intercurrent events:**
  - Discontinuation of treatment prior to the End of Treatment Assessments on Days 25, 26 and 28: Participants who discontinue treatment prior to the one month DBPCFC part 2A, or who miss more than 20% of treatment doses throughout the study, or who miss medication doses for  $\geq 3$  consecutive days in the seven days prior to the one month DBPCFC part 2A due to any reasons other than adverse events
  - Intake of rescue medication prior to DBPCFC conducted at one month
- **Summary measure:** Difference in the proportion of responders between remibrutinib and placebo

Supplementary estimands to the primary estimand are defined in [Section 12](#).

[figure not shown]
## 2.2 Secondary estimands

Not Applicable.

### 3 Study design

Figure 3-1 Study Overview

\* Day 2 visit only needed for site participating in the BAT laboratory assessment

This is a Phase 2 multi-center, randomized, participant- and investigator- blinded, placebo controlled study to assess the safety and clinical efficacy of four dosing regimens of oral remibrutinib versus placebo (CCI for one month (4-5 weeks); CCI for one month (4-5 weeks); CCI for one month (4-5 weeks); placebo for 3 weeks followed by remibrutinib CCI for 1-2 weeks; and placebo for one month (4-5 weeks) in adult participants with a medically confirmed diagnosis of IgE-mediated peanut allergy. Approximately 72 participants will be randomized in this study to one of the five arms (randomization ratio of 2:2:2:1:1). Participants initially assigned to the 3-week placebo arm will receive the first dose of blinded remibrutinib treatment at the Day 22 visit. CCI

The study will include the following:

- 1. Screening period (duration of 4 weeks with 3 required visits):** Written informed consent will be obtained before any study-related assessments or procedures are performed. Consented participants will be assessed for study eligibility during the Screening Visit 1 and will need to meet all eligibility criteria for this visit in order to progress to Screening Visits 2 and 3 (DBPCFC parts 1A and 1B), conduct of the double-blind, placebo-controlled food challenge.

To minimize bias in reaction for individual participants, sequence in which allergen or placebo material is provided will be determined by IRT. Participants who receive placebo-allergen challenge material during DBPCFC part 1A will receive peanut-allergen challenge material during DBPCFC part 1B; while those who receive peanut-allergen challenge material during DBPCFC part 1A will receive placebo-allergen challenge material during DBPCFC part 1B. The participant and all study staff, except the unblinded pharmacist/staff member who will re-constitute the allergen, will be blinded to which visit administers which (allergen or placebo).

Those participants who meet threshold requirements for allergen challenge (as described in [Section 5.1](#)) will proceed to the treatment randomization visit and study treatment period.

To ensure participants meet inclusion/exclusion criteria for exposure to both peanut-allergen and placebo-allergen, unblinding of the food challenge will be disclosed a minimum of 30 minutes following the maximum dose of DBPCFC part 1B at screening visit 3.

2. **Treatment period:** The treatment period is approximately one month long and can range from 4-5 weeks due to the visit windows allowed as well as due to the need to collect end-of-treatment data across 3 visits that have required minimum spacing between them.

Study participants will be seen in the clinic on Day 1 (treatment randomization), Day 8, and Day 22, for on-treatment clinic visits and drug dispensation. Study participants will also be seen in the clinic for three end-of-treatment visits, which collect primary and secondary one month endpoint data, collectively. These will occur on Day 25, Day 26 (DBPCFC part 2A) and Day 28 (DBPCFC part 2B).

The study treatment will begin on Day 1 at the randomization visit and will continue until the CCI of the DBPCFC part 2B end-of-treatment visit. The study treatment is three placebo -matched tablets administered by the participant at home CCI

Participants will continue study drug dosing CCI from Day 1 visit through the CCI dose of their Day 28 (DBPCFC part 2B) visit. The CCI administration of study drug on Day 28 (DBPCFC part 2B) will be the last dose.

There is a minimum of 2 days (48 hours) needed between the DBPCFC parts 1 and 2. Given the need for flexibility to accommodate holidays and weekends, participants will have a window of plus 2 days for all three end-of-treatment visits on Days 25, 26 and 28, which, if maximized, may extend treatment to up to 34 days. Treatment will not exceed 34 days. Participants will be encouraged to try to maintain the visit schedule as written and avoid utilizing windows as much as possible to keep the study treatment period as short as possible.

3. **End of Study Visit and Follow Up Period:** After completion of Day 28 (DBPCFC part 2B) visit, participants will return to clinic 3 days post-last-dose on Day 31 for the end of study visit, which will include post-dose assessments and study evaluations including safety, pharmacokinetics, post-treatment biomarkers, etc. (See [Table 8-1](#)). The end-of-study visit should not be earlier than 3 days (72 hours) after the last dose of study drug to facilitate proper PD/biomarker analysis. Additionally, a 30-day post-last-dose safety call will be placed to the participant and will complete participation in the study.

